### **c.8.3. Specific Analyses for the Individual Study Aims**

**Primary Aim 1:** For the primary and secondary hypotheses, one-sided tests for non-inferiority will be applied as our goal is to show that the performance of the children in SC-TF-CBT will demonstrate comparable improvements to children in standard TF-CBT. For this non-inferiority test, the null hypothesis is written as  $H_0: \mu_1 - \mu_2 > r^*$ , where  $\mu_1$  denotes the average improvement in standard TF-CBT and  $\mu_2$  denotes the average improvement among children in SC-TF-CBT, and  $r^*$  represents the clinically significant difference expressed as common standard deviation units. The test will be applied to child outcomes, acceptability/satisfaction levels and parent outcomes that will be measured at post-treatment and at 6- and 12-month follow-up respectively.

Rejection of the null hypothesis will indicate that treatment outcomes of SC-TF-CBT are comparable to those from standard TF-CBT. For child and parent outcomes only, we will further apply GLM with repeated measures to detect whether the two treatment groups perform differently at any one time point. We will also document the percentage of responders to Step One and numbers and reasons for trigger and switch.

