**c.9. Sample Size Considerations and Power Analyses.** We will enroll a total of N=216 subjects with a 1:1 randomization between SC-TF-CBT and standard TF-CBT. Based on our successful track record in obtaining post and follow-up data in our R34 SC-TF-CBT trial (only 3.77% missing post- data, and 6.1% missing 3-mo. follow-up data, N=53), and the PIs previous child trauma clinical trial with a 1-year follow-up (8.57% attrition), we conservatively anticipate 15% attrition at post-assessment resulting in 184 subjects (92 per group) and a 10% lost to follow-up at 6- and 12-months resulting in 166 subjects (83 per group) and 150 subjects (75 per group), respectively. Sample size requirement was determined by CEA for Primary Aim 4 and it also provides sufficient power for Primary Aims 1 to 3 under various assumptions. **Primary Aim 1**, Hypothesis 1.1, the study will have 80% power to show that SC-TF-CBT is at least as effective as standard TF-CBT. This assumes an alpha of .05, sample size of 92 per group after attrition and a difference of 0.41 SD units or less as unimportant. We expect to maintain the same power of 80% in testing the hypothesis (1.2.) that focuses on the outcomes at follow-up (6- and 12-months). Though we may lose an additional 10% of participants at each follow-up point, reduction in measurement error through repeated measures and use of multiple imputation method will mitigate the sample size loss. For **Primary Aim 2**, 80% power will be achieved for detecting responding rates difference between 62% and 30%, 72% and 40%, or 80% and 50%. This assumes that we divide the patients into two equal size groups based on the tailoring variable value with a total of 92 patients (SC-TF-CBT condition only). For **Primary Aim 3**, we will have >80% power to detect a small to moderate effect (0.29) in a unidirectional bivariate latent different score model with complete longitudinal observation for the 184 children under both conditions (for analyses involving CPTCI, the detectable effect size is 0.33). For the secondary hypothesis 3.2., we have moderate power (.57) to detect different strengths of the unidirectional prediction between the two conditions (e.g., 0.15 vs 0.45 or .00 vs .30; for the CPTCI, the power for the same comparisons is .55). For **Primary Aim 4**, the study will have 80% power to detect cost differences between SC-TF-CBT and standard TF-CBT, assuming medium effect size (.5), an alpha of .05 and sample size of 92 per group. The sample size will also be sufficient to maintain 80% power to detect a medium effect size for children with low values for the tailoring variable, and to detect a large effect size for children with high values.

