## Amendment to the analysis plan 2.11.2022

**Aim 1.** We applied linear mixed-effect models (LME; SAS Institute Inc, 2015) with repeated measures to detect whether the two treatments performed differently at post-, 6- and 12-month assessments. Instead of 5% alpha we used a more stringent 2.5% alpha (Piaggio et al, 2012) for the non-inferiority analysis with the .41 margin. For the non-inferiority margin for the PCL-5, the clinically significant change threshold is 10 points although adult PTSD trials have used -5 (Foa et al., 2019) to -10 (Mathersul et al., 2019) points. We used -8.8 as the margin which was based on an expert panel and prior studies with adults (Acierno et al., 2017). Due to attrition (27.87%) being higher than planned (15%) and enrollment (N = 183) lower than the planned enrollment (N = 216), the power analysis was based on the actual randomization of 183 participants (SC-TF-CBT=91; standard TF-CBT=92).

**Aim 2.** We used backward stepwise logistic regression with predictors with  $p < .01$ . Besides predictors in the unadjusted model, demographics including children gender, age and race were included in the partially adjusted

model. In addition, three child primary outcomes were added for the full adjusted model.

**Aim 3.** Instead of LDS we used Linear mixed-effect models (LME) with repeated measures were used to detect whether the potential mechanisms of change declined significantly over time and whether the rate of change differed by treatment group with standard TF-CBT coded as 0 and Step One responders coded as 1. Further, we tested mediation and moderated mediation. If moderated mediation was not found mediation was tested with two regression equations: the first equation included mediators regressed on treatment condition and outcome variables at baseline; the second equation included outcomes regressed on treatment condition, mediators, and outcome variables at baseline. If there was no evidence of significant mediation, linear regression model (OLS) was applied to test the linear estimates as predictors for both outcome (TSCYC-PTS and CSDS-P).

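### The amendment bases Aim 1 power on all 183 randomised children with nothing taken off for attrition, so the 80% in c.9 is unsupported for the amended trial, though not shown to be out of reach

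*Combined protocol and SAP*

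**What the plan says.** Section c.9 plans 216 children, 15% attrition at post-assessment (184 left) and a further 10% loss at each follow-up, leaving "166 subjects (83 per group) and 150 subjects (75 per group), respectively". For Hypothesis 1.1 it states 80% power at an alpha of .05, with a "sample size of 92 per group after attrition and a difference of 0.41 SD units or less as unimportant". For Hypothesis 1.2, on the 6- and 12-month outcomes, it says "We expect to maintain the same power of 80% in testing the hypothesis (1.2" and so on, on the ground that "reduction in measurement error through repeated measures and use of multiple imputation method will mitigate the sample size loss". No size is given for either gain.

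Section c.8.3 makes the Aim 1 tests one-sided and says that the margin "represents the clinically significant difference expressed as common standard deviation units". It does not say whether that is the SD of the score or of the improvement.

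The Aim 1 paragraph of the 2.11.2022 amendment keeps the .41 margin and changes the level: "Instead of 5% alpha we used a more stringent 2.5% alpha". It reports 27.87% attrition against 15% planned, and 183 enrolled against 216 planned. Because of these two shortfalls, it says, "the power analysis was based on the actual randomization of 183 participants", 91 in SC-TF-CBT and 92 in standard TF-CBT. It gives no resulting power, no observed number by arm or visit, and no correlation or imputation assumption.

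**The concern.** The 92 per group in c.9 is what remains after attrition. The 91 and 92 in the amendment are counts before attrition. The two pairs are almost equal, so the amended basis looks as if it preserves the planned power, although the sentence that introduces it gives higher attrition as one of its reasons.

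The only Aim 1 power figure in the documents is the 80% in c.9. A reader who carries it over, or who takes 183 as the effective sample, will overrate the precision of any outcome or visit where non-inferiority is not shown. Such a reader may take an inconclusive result for evidence of inferiority.

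**Working it through.** **Inputs.** Margin 0.41 SD (c.9 and amendment). One-sided 2.5% (amendment). 92, 83 and 75 per group (c.9). 91 and 92 randomised, 27.87% attrition (amendment). True difference 0 is an assumption; the documents give none.

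**Formula.** Power = Φ(0.41 / √[f(1/n₁ + 1/n₂)] − 1.96), with f = 1 when nothing is adjusted for.

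**Reproducing c.9.** With 92 per group, √(2/92) = 0.1474 and 0.41/0.1474 = 2.781.
- One-sided 2.5%: Φ(2.781 − 1.960) = 79.4%, which matches the stated 80%.
- One-sided 5%, read literally: Φ(2.781 − 1.645) = 87.2%, which does not.

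The 80% in c.9 thus already corresponds to one-sided 2.5%. On that reading the shortfall below comes from enrolment and attrition, not from the change of alpha.

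**What 27.87% is.** 51/183 = 0.2787, so it fits a share of those randomised; 183 − 51 = 132, or 66 per arm if split evenly (assumption; no split is given). The amendment does not say whether the 51 left treatment or lack outcomes, or at which visit. Section c.10 plans to assess children who drop out, so the two counts can differ.

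**Loss rates in c.9 applied to 183.** 183 × 0.85 = 155.6; × 0.9 = 140.0; × 0.9 = 126.0. That is about 78, 70 and 63 per arm.

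**Unadjusted power, one-sided 2.5%:**

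| Children per arm | Source | Power |
|---|---|---|
| 92 | c.9, post | 79.4% |
| 83 | c.9, 6 months | 75.2% |
| 75 | c.9, 12 months | 70.9% |
| 91/92 | amendment, no loss | 79.2% |
| 78 | 183 with c.9 losses, post | 72.6% |
| 70 | 183 with c.9 losses, 6 months | 67.9% |
| 63 | 183 with c.9 losses, 12 months | 63% |
| 66 | 51 missing at the visit, even split | 65.4% |

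Using the noncentral t distribution lowers these by less than one point (79.0% at 92, 78.8% at 91/92, 64.7% at 66). Unadjusted 80% needs 2 × (2.8016/0.41)² = 93.4, so 94 observed per arm.

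**With baseline adjustment.** Let ρ be the correlation of baseline and outcome, with equal variances. The residual variance is (1 − ρ²) of the score variance. If the margin is in score SDs, f = 1 − ρ². If it is in SDs of improvement, whose variance is 2(1 − ρ) of the score variance, f = (1 − ρ²)/[2(1 − ρ)] = (1 + ρ)/2. The documents give no ρ; the values below are assumed.

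| Per arm | Unit of margin | ρ = .3 | ρ = .5 | ρ = .6 |
|---|---|---|---|---|
| 78 | score SD | 77% | 84% | 89% |
| 78 | SD of improvement | 89% | 84% | 82% |
| 66 | score SD | 69% | 78% | 84% |
| 66 | SD of improvement | 83% | 78% | 75% |

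At 66 per arm, 80% needs f ≤ 33 × (0.41/2.8016)² = 0.707. That means ρ ≥ .54 for score SDs but ρ ≤ .41 for SDs of improvement, so the undefined unit decides even the direction in which correlation acts.

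**What this means for a result.** The largest observed difference that still shows non-inferiority is 0.41 − 1.96√[f(1/n₁ + 1/n₂)]. Unadjusted, it is 0.41 − 0.290 = 0.12 SD at 91/92. If 66 per arm are observed, it is 0.41 − 0.341 = 0.07 SD. With ρ = .5 at 66 per arm (f = .75 under either unit) it is 0.41 − 0.341 × 0.866, about 0.115 SD.

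**The case against.** The strongest reply is that the amendment claims no power at all. It prints a basis and no figure, and the 80% stays in c.9. That is true: the defect is a basis that ignores attrition and a missing number, not a false sum.

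Second, the unadjusted figures may be too low. Section c.8.2 plans to control for baseline measures. The measures table and c.6.6 collect the parent-rated primary outcomes, TSCYC-PTS and CSDS-P, at mid-treatment and at sessions or parent-child meetings, so a child who misses the post visit may still have post-baseline data. Section c.10 plans multiple imputation. This stands: the unadjusted figures are lower scenarios, and at 78 per arm five of the six adjusted cases exceed 80%. But no document states how much any of this recovers, and the amendment does not say whether its mixed model keeps the baseline adjustment.

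Third, the Aim 4 paragraph of the amendment refers to non-inferiority results, so power may seem beside the point. For outcomes and visits where non-inferiority was shown, it is. The documents do not show whether any outcome or visit failed.

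A reader might infer that the trial had only 65% power, or that its non-inferiority findings are unsafe. Neither follows. The 65% needs every one of the 51 to lack the outcome at the analysed visit, an even split and no adjustment. Low power does not raise the chance of declaring non-inferiority falsely.

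**Conclusion.** The point holds in a limited form. The 80% in c.9 is for observed children; the amendment replaces them with randomised children and deducts nothing. Unadjusted, its 183 give about 79% only with complete outcomes, and about 73%, 68% and 63% at the three visits under the loss rates in c.9. With adjustment at assumed correlations of .3 to .6, the range is 77% to 89% at 78 per arm and 69% to 84% at 66 per arm. The 80% is therefore unsupported for Hypotheses 1.1 and 1.2 in the amended trial, but not shown to be unattainable.

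All figures assume a true difference of 0. They apply to outcomes tested with the 0.41 SD margin, not to the PCL-5, for which the amendment sets its own margin of −8.8 points. The textual point is firm; the size of the shortfall is not, because the meaning of the 27.87%, the SD unit and the correlation are all unstated.

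**What to change.** 1. In the amendment and the report, state what the 27.87% counts and at which visit. Give the observed number per arm at post-treatment, 6 and 12 months. Restate Aim 1 power at one-sided 2.5% on those numbers, naming the SD unit of the 0.41 margin and any correlation or imputation gain assumed. Do not carry the 80% in c.9 over for Hypothesis 1.1 or 1.2. Report each Aim 1 confidence interval against its margin as the measure of achieved precision; with the data already analysed, this tells the reader more than a restated power.

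2. As a separate, minor improvement that does not bear on the power claim, report one further Aim 1 mixed model. Section c.4 balances randomisation within four cells (internalizing T-score above 71 or not, critical events score above 16 or not), but no section names them as Aim 1 model terms. Section c.8.2 enters site only if a baseline test gives p < .10. The extra model would hold the four cells as fixed terms, keep the baseline outcome, and include site whatever that test shows. Label it a post-amendment sensitivity analysis, since results were known when the amendment was written.

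The cost is some wording, one table and one model on existing data; no new patients or data. The stated power may be less favourable, and the extra model may differ from the main one and would then need discussion.

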**c.1.2. Candidate First-Stage Tailoring Variables.** An exploratory aim of the R34 was to explore differential characteristics of Step One responders/non-responders to identify potential first-stage tailoring variables. Based on prior literature and our clinical experience, we first explored differences in child variables (PTSD symptoms, internalizing and externalizing problems, depression, polytrauma (>1 traumatic event), interpersonal/non-interpersonal trauma, and age), parent variables (PTSD, depression and parenting stress) and environmental factors (treatment barriers) between Step One responders/non-responders. Two measures that showed substantial differences between responders and non-responders were internalizing problem T-scores and critical life events regarding barriers to treatment. We further applied classification tree method[78] to find the optimal cutoff values that maximally distinguished responder/non-responders after Step One. Regarding total internalizing T-scores, those children (16/49=32.7%) with a score >71 had a response rate of 56.3%, and those with a score ≤71 had a response rate of 87.9% ( $X^2=6.19$ ,  $p=.01$ ). Regarding critical life events, those children

(28%) with a score  $>16$  had a response rate of 44.4%, and those with a score  $\leq 16$  had a response rate of 82.6% ( $X^2=4.66, p=.03$ ). We recognize that given the small sample size, some of the results did not reach significance especially when adjusting for multiple comparisons. However, high internalizing problems is consistent with the literature suggesting that these children may need more intensive treatment [79, 80] and our qualitative findings are consistent with critical life event barriers as a theme for Step One non-responders. We considered externalizing problems as a first-stage tailoring variable since non-inferiority was not supported; however, there was not a significant difference between responders/non-responders and externalizing problems after Step One; nor was there a clear significant optimal cutoff value. Further, since GLM results and percentages of those above the clinical cutoff revealed no significant differences between SC-TF-CBT and TF-CBT at post- and follow-up, the evidence did not support externalizing problems as a tailoring variable. These results provide suggestive evidence of effect moderation and a preliminary establishment of candidate first-stage tailoring variables to be tested in the proposed application.

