**Primary Aim 2:** To examine tailoring variables that could be used to individualize the decision of which children should be assigned at baseline to SC-TF-CBT versus standard TF-CBT, we will compare the responders/non-responders of Step One with regard to the value of the tailoring variables. Based on results from pilot studies, we hypothesized that children with more internalizing problems at baseline and those from families with potential life event barriers are less suitable for SC-TF-CBT. A Chi Square test will be first applied to evaluate the association between the dichotomized candidate tailoring variable and responding status. Next, we will use GLM, in which responding status will be treated as the dependent variable and tailoring variables as continuous predictors. To further quantify the relation between the value of the tailoring variables and the propensity of not responding to Step One, we will include in the GLM the products of the tailoring variables to evaluate their interactions. Demographics will also be controlled in the model. While it was not a primary aim, we will further explore whether race/ethnicity or gender moderate the dropout rate and treatment outcomes (see 6.). This will be done in a separate analysis where interactions with treatment condition are included.

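### The amended Aim 2 selection at p<.01 does not protect the two hypothesised tailoring variables, and the 80% power in c.9 was not restated for that threshold

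*Combined protocol and SAP*

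**What the plan says.** Hypothesis 2.1 (section 2) names internalizing problems and perceived critical life events as the characteristics expected to go with non-response to Step One. Section c.4 blocks the randomization on both, with cut-offs of 71 and 16.

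The Aim 2 plan in c.8.3 starts from the two variables: "A Chi Square test will be first applied to evaluate the association between the dichotomized candidate tailoring variable and responding status". A generalized linear model follows, with response as the outcome, the tailoring variables as continuous predictors, their products, and demographics. No step removes a variable.

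Section c.9 states that "80% power will be achieved for detecting responding rates difference between 62% and 30%, 72% and 40%, or 80% and 50"%, on the assumption that "we divide the patients into two equal size groups based on the tailoring variable value with a total of 92 patients (SC-TF-CBT condition only"). No alpha is given for Aim 2. The .05 in that section belongs to Aim 1 ("This assumes an alpha of .05, sample size of 92 per group after attrition") and Aim 4.

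The amendment of 2.11.2022 says for Aim 2: "We used backward stepwise logistic regression with predictors with" p<.01, followed by partially and fully adjusted models. It does not list the candidate predictors, say whether .01 is an entry or a retention rule, or say that the two hypothesised variables stay in regardless. It revisits power only under Aim 1, where it reports 183 randomized (91 to SC-TF-CBT) and 27.87% attrition.

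**The concern.** A hypothesis about two named variables is answered by estimating and reporting those two effects. Selection at p<.01 replaces that with a rule under which either variable can disappear. A variable that drops out may then be reported as not predictive when the comparison was simply short of power. One that survives does so partly because its estimate came out large, so its coefficient is biased away from zero and its nominal p-value is too small.

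Aim 2 is meant to inform which children start with Step One, and the Aim 4 text in c.8.3 makes a subgroup cost analysis depend on whether the tailoring variables work. A threshold stricter than .05, applied to fewer children than planned, also raises the question of what remains of the stated 80%.

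**Working it through.** **Inputs.** From c.9: response-rate pairs 62/30, 72/40 and 80/50%, and 92 SC-TF-CBT children split 46/46. From the amendment: threshold .01, 91 randomized to SC-TF-CBT, attrition 27.87%. From c.1.2: 32.7% of pilot children (16/49) "with a score >71 had a response rate of 56.3"%, against 87.9% at or below the cut-off; for critical life events, 28% above the cut-off, with response 44.4% against 82.6%. Assumptions: two-sided alpha .05 for the stated design, and overall attrition applied to the SC-TF-CBT arm, 91 × (1 − 0.2787) = 65.6, about 66.

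**Formula.** Two-proportion test with group sizes n1 and n2 and weighted mean rate p̄:

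se0 = √[p̄(1−p̄)(1/n1+1/n2)], se1 = √[p1(1−p1)/n1 + p2(1−p2)/n2], power = Φ[(d − z·se0)/se1].

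Here d = |p1−p2|, less ½(1/n1+1/n2) when continuity-corrected; z is 1.960 at .05 and 2.576 at .01.

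**Stated figure, 62/30 with 46 per group.** p̄ = .46, se0 = √(.2484 × 2/46) = .1039, se1 = √(.4456/46) = .0984.
- At .05, uncorrected: (.320 − .2037)/.0984 = 1.18, power 88%.
- At .05, corrected: d = .320 − .0217 = .2983, giving .96, power 83%.

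Over the three pairs the range is 81-88%, so 80% is attained. Uncorrected two-sided .025 gives 79-82%, which is closer, so the alpha behind the stated figure cannot be recovered with certainty.

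**Same design at .01.** Uncorrected: (.320 − .2677)/.0984 = .53, power 70%. Corrected: (.2983 − .2677)/.0984 = .31, power 62%.

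**All three c.9 pairs at .01:**

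| Children | Split | Uncorrected | Corrected |
|---|---|---|---|
| 92 | equal | 68-71% | 59-63% |
| 91, no attrition | equal | 67-70% | 58-62% |
| 92 | 28-33% high | 58-65% | 48-56% |
| 66 | equal | 49-52% | 38-41% |
| 66 | 28-33% high | 40-47% | 29-37% |

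**Pilot response rates with the pilot split, at .01:**

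| Variable | 92, uncorrected / corrected | 66, uncorrected / corrected |
|---|---|---|
| Internalizing (32.7% high) | 78 / 70% | 61 / 50% |
| Critical life events (28% high) | 85 / 79% | 69 / 58% |

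**Continuous coding.** A simulated logistic model with one normal predictor and a linear logit, its slope set to reproduce the c.9 rates at a median split, gives at .01 about 86-91% with 92 children and 67-77% with 66 (Wald to likelihood-ratio test).

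**Pilot results against the rule.** The pilot chi-squares of 6.19 and 4.66 on one degree of freedom give p = .0128 and .031. Neither is below .01.

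**The case against.** Much can be said for the sponsor. The amendment's wording is brief. Unlike Aims 3 and 4, the Aim 2 paragraph does not say that it replaces anything, so the planned chi-square test of each dichotomised variable is not expressly withdrawn. The 80% in c.9 belongs to that kind of two-group comparison, and the arithmetic behind it is sound. The amended method is logistic regression; if the scores entered as continuous, power is higher than the dichotomised figures suggest.

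The smaller sample is also an assumption. Attrition is reported under Aim 1, without arm or time point, while Step One response is assessed after Step One (week 6 in Table 1), so later loss need not be loss to Aim 2. The trial's own high-score share is not given either.

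These points stand, and they rule out two stronger readings. A reader might infer that the p<.01 rule itself cuts power to 30-50%. It does not: alone it gives about 59-71%, and the lower figures need about 66 children, with the bottom of the range also needing the pilot split and a continuity correction. A reader might also infer that a real tailoring variable is more likely than not to be dropped. That fails under the rule alone with an equal split, at the pilot's rates and under continuous coding. In the other direction, the pilot rates come from cut-offs chosen to separate responders from non-responders, so power based on them may be optimistic.

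None of this answers the central point. Under either reading of .01, nothing in the amendment keeps the two named variables in the model.

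**Conclusion.** The concern holds as a gap in protection and in the stated power. Two variables that were hypothesised, blocked on and planned for modelling can be removed on their p-values, and the pilot findings that motivated them would not have met the criterion. (The pilot was smaller, with 49 children in the internalizing comparison, so this illustrates how strict the threshold is; it does not predict the trial's result.)

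For the dichotomised comparison in c.9, the threshold alone takes power from 81-88% to about 59-71%. This does not depend on attrition: with all 91 randomized children and an equal split it is still 58-70%. About 38-52% requires the reported attrition to apply to this arm, and about 29-47% requires the pilot's 28-33% high-score share as well. At the pilot's own rates and split, power at .01 is about 70-85% with 92 children and 50-69% with 66, and continuous modelling raises it further.

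The baseline of .05 is borrowed from Aims 1 and 4. It should not be described as the planned Aim 2 level, because the documents state none.

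**What to change.** Keep both hypothesised variables in the logistic model as continuous predictors whatever their p-values. Report each estimate with its confidence interval and a test at a stated alpha; .05 would match c.9 for Aims 1 and 4. Confine stepwise selection at p<.01 to other predictors and label those results exploratory. List the candidate set, say whether .01 governs entry or retention, and say whether the chi-square tests were kept. Restate Aim 2 power for the alpha used, the number of SC-TF-CBT children with a Step One response assessment, and the observed split.

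The cost is a few sentences in the amendment and one refit on existing data. The stated power will be less favourable.
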